## 4. STUDY DESIGN

Multicenter, multinational, double-blind, randomized (2:1), placebo-controlled Phase III study to investigate the efficacy and safety of 100 mg FAB122 (former TW001) once daily as oral formulation in ALS patients.

Subjects will be screened to assess whether they comply with all enrolment criteria. Approximately 300 patients will be randomized to 100 mg FAB122 or matched placebo in a 2:1 ratio. Patients will be stratified by;

- 1) their ALS progression rate at the start of the study (the slope ALSFRS-R score from time of first symptoms till Screening <1.0 vs.  $\geq 1.0$ ),
- 2) additional co-medication for ALS (a. riluzole, b. no riluzole).

Riluzole (100 mg/day or less) may be used as background (add-on) therapy. Patients on riluzole should be on stable doses at the start of the trial and for at least 30 days before the initiation of the study drug. It will not be allowed to initiate riluzole therapy during the trial. Additional supportive Standard Of Care (SOC) treatments will be allowed in all patients and will be standardized as much as possible.

Subjects will receive double-blind treatment up to a maximum of 72 weeks. The study is planned to continue until the last randomized subject has reached 48 weeks of follow up (or has reached an intercurrent event) AND the first one third of the subjects randomized (100) have reached 72 weeks of follow up (or has reached an intercurrent event). Subjects who discontinue treatment before week 72 will be followed as much as possible according to the planned visit schedule. In case of sanitary restrictions due to COVID-19 pandemic, home visits might be performed (for more details, see annex 4).

[figure not shown]
Subjects will visit the clinic at Screening, Baseline, Week 4, Week 12, and every 12 weeks thereafter. Monthly telephone visits are performed in between the visits to the clinic until Week 48.

Blood sampling for FAB122 plasma concentrations will be done in ~90 subjects treated with the study drug.

After a subject completed the study (max at 72 weeks), he/she will be offered the possibility to roll over in an open label extension trial in which all subjects will be offered to receive FAB122.

The end of the trial will correspond to the last subject last visit per the trial schedule.

The study flowchart is presented in the Figure 2.

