### 8.3.1. Population and profiling PK Analysis

FAB122 plasma concentration-time data will be subjected to a population PK analysis using nonlinear mixed-effects modelling. Blood sampling for FAB122 PK analysis will be done in ~90 subjects. Of those ~30 subjects will participate in a PK profiling sampling schedule at baseline, week 4 and week 48 and a population PK sampling schedule at baseline, ~60 subjects participate in the population PK sampling schedule at baseline, week 4 and week 48. Plasma concentrations of all these PK samples may be included in the population PK analysis. For this analysis, the data may be combined with results of other studies. The aim of the population PK analysis is to develop a compartmental model of the FAB122 concentration vs. time profiles, which will provide a good understanding of the inter-subject and intra-subject (if possible) variability in the exposure. Available subject characteristics (such as demographics, laboratory variables and co-medication) will be tested as potential covariates affecting PK parameters.

It is estimated that about 90% of the patients included in this study will concomitantly receive riluzole treatment. Results from pharmacokinetic profiling and population PK analysis will therefore also be used to study the effect of riluzole on FAB122 concentrations and vice versa. Therefore, mean plasma PK parameters of subjects who received FAB122 and riluzole will be compared to those of subjects who received riluzole and placebo.

In addition, blood sampling for the determination of riluzole concentrations will be done in the subjects included in FAB122 PK sampling in baseline and week 4 (~60 subjects). Mean plasma Ctrough and Cmax levels of subjects who received riluzole and FAB122 at

---

baseline visit and after 4 weeks of treatment with FAB122, as well as changes in these metrics between baseline and week 4 will be compared to those of subjects who received riluzole and placebo. If needed and feasible, modelling will be applied to support statistical analysis methods.

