### **5.6.1 Primary analysis**

The primary endpoint is defined as the change from baseline in total ALSFRS-R score after 48 weeks (primary timepoint).

For the primary analyses, a placebo (reference) multiple imputation (pMI) will be applied to impute missing data for any patients (i.e. from both treatment arms) who discontinue treatment early, irrespective the reason for drop-out (only when due to intercurrent events with unknown cause), and for which no data was collected after treatment discontinuation. The pMI method assumes the statistical behavior of placebo- and drug-treated patients after dropout is the statistical behavior of placebo-treated patients. A total of 20 imputed data sets will be created.

Before applying the statistical model to the primary endpoint, intercurrent events will be handled following the rules specified in Section 5.2.

The primary endpoint will be analyzed using a mixed model for repeated measures (MMRM), considering ALSFRS-R is assessed at multiple timepoints. The average treatment effect (lsmeans) and the treatment difference (estimand) of the change from baseline ALSFRS-R total score at 48 weeks will be extracted from the results from this model and presented together with the 95% confidence interval and p-value. Other timepoints will also be presented.

The model will include factors for treatment, time, treatment-by-time interaction, the stratification factor concomitant use of riluzole (yes/no), baseline ALSFRS-R score and the stratification factor slope of disease progression as fixed effects. An unstructured (UN) covariance matrix will be used in the model. If the model does not converge, the structure will be adapted to respectively AR(1), Toeplitz or Compound Symmetry (CS). The results of the 20 imputed data sets will be combined to obtain the final estimate of the treatment difference with 95% confidence interval and p-value.

An example SAS code which can be used as basis is as follows:

```
proc mixed data=<data>;
  class trt time riluse;
  model cfb=trt time trt*time riluse base disslope / ddfm=kr;
  repeated time/ subject=patient type=un;
  lsmeans trt*time/cl;
run;
```

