### **ALSFRS-R score**

Absolute and change from baseline in total ALSFRS-R score after 24 (full group and subgroup) and 72 weeks (subgroup only) will be presented by treatment group in summary tables. Note that results after 12, 48 and 60 weeks for full group/subgroup as available will also be presented by treatment group in the same summary table. The statistical analysis is as described in the section on the primary endpoint.

The proportion of patients with change from baseline in ALSFRS-R score at 24, 48 and 72 weeks will be presented in categories for each treatment group. Categories will include change  $\geq 0$ , change between  $< 0$  and  $\geq -1$ , change between  $< -1$  and  $\geq -2$  etc. A Chi-squared test will be performed, and the p-value added to the table.

The slope of the decrease in ALSFRS-R total score over time at 24, 48 and 72 weeks will be calculated and presented in summary tables. Per treatment arm, slopes will be determined using an MRMM model on the change from baseline, with independent variables treatment group, baseline value, time and treatment\*time interaction. Slopes for each treatment group and slope difference between treatments will be presented. No individual per-patient slopes will be presented.

---

 Where date of death is taken from the Survival follow-up form.

Change from baseline in ALSFRS-R subscale scores will also be calculated after 24, 48 and 72 weeks for the following subscales:

- Bulbar function (question 1-3 of the ALSFRS-R);
- Fine motor function (question 4-6 of the ALSFRS-R);
- Gross motor function (question 7-9 of the ALSFRS-R)
- Respiratory function (question 10-12 of the ALSFRS-R);

Summary statistics for the change from baseline in the above subscale scores will be presented by treatment group and overall, again separately for the full group and the subgroup.

In addition, a similar statistical model as for the primary endpoint will be utilized for analyzing the change from baseline for the subscale scores.

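### The ALSFRS-R slope model leaves out both randomisation strata and does not state its covariance, so the width of its intervals is not assured

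*SAP*

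**What the plan says.** SAP 5.6.2 (ALSFRS-R score) gives the slope analysis its own variable list: "slopes will be determined using an MRMM model on the change from baseline, with independent variables treatment group, baseline value, time", plus the treatment-by-time interaction. It does not refer back to the primary model. The analysis of change in total score and the models for the subscales, SVC, HHD, ALSAQ-40 and VAS all do. On output, it adds "No individual per-patient slopes will be presented".

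Protocol section 4 stratifies randomisation by "their ALS progression rate at the start of the study" (below 1.0 against 1.0 or more) and by "additional co-medication for ALS (a. riluzole, b. no riluzole").

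Other analyses use these factors:

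- The primary model (SAP 5.6.1) includes "the stratification factor concomitant use of riluzole (yes/no), baseline ALSFRS-R score and the stratification factor slope of disease progression as fixed effects".
- The CAFS ANCOVA, where it is used, includes both factors as covariates.
- The RMST, Cox and stratified log-rank analyses of survival time adjust for the stratification variables.

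On covariance, SAP 5.6.1 says of the primary model: "An unstructured (UN) covariance matrix will be used in the model". If it does not converge, the order is AR(1), Toeplitz, then compound symmetry. Nothing equivalent is written for the slope model. It is also not said whether time is continuous. In the primary example code, time is a class variable, and that form yields no slope.

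**The concern.** Pre-study progression rate is an obvious candidate predictor of on-study slope, and it was balanced by design. When allocation is stratified and the model ignores the strata, the between-stratum variation stays in the error term although it no longer affects the comparison of arms. The reported error is then larger than the real one.

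The silence on covariance can work the other way. Patients differ in slope. A working covariance that cannot represent this, such as compound symmetry, treats within-patient points as far more informative about slope than they are, and the reported error is then too small.

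At stake is whether the interval around the slope difference at 24, 48 and 72 weeks can be taken at face value.

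**Working it through.** **The plan's own figure.** No standard error or power is stated for the slope, so the primary calculation is reproduced first. Placebo n = 1.5 × (1.960 + 1.282)² × 7.5² / 3.0² = 98.5, so 99, total 297 (stated 300). With 200:100, SE = 7.5 × √(1/200 + 1/100) = 0.919 and 3.0/0.919 − 1.96 = 1.306, which gives power 90.4% (stated 90%). Both reproduce.

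**Inputs from the documents.** ALSFRS-R every 4 weeks from week 4 to week 48 (12 post-baseline points, Protocol 8.1.1); 200:100 patients; SD 7.5 at week 48; about 90% on riluzole (Protocol 8.3.1).

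**Assumptions not in the documents.** Slope SD s_b, residual SD s_e, share R² of slope variance explained by the strata, 30% fast progressors in the simulations, complete data.

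One visit interval is 28/30.4375 = 0.920 months, so Sxx = 0.920² × 143 = 121.0 month².

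**1. Strata omitted, covariance adequate.** Per patient, the model assumes slope variance s_b² + s_e²/Sxx. Under stratified allocation the variance that matters is (1 − R²)s_b² + s_e²/Sxx. The ratio of reported to real SE is the square root of their quotient.

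- Low end (s_b 0.3, s_e 2.5, R² 5%): √(0.1417 / 0.1372) = 1.016.
- High end (s_b 0.7, s_e 1.5, R² 30%): √(0.5086 / 0.3616) = 1.186.
- Scaled to SD 7.5 at week 48 with s_e 2: s_b² = (56.25 − 2 × 4)/11.04² = 0.396. Reported SE = √(0.015 × (0.396 + 4/121.0)) = 0.0802. With R² 20%, real SE = √(0.015 × (0.317 + 0.033)) = 0.0724. The excess is 11%.

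A simulation of 1,000 trials with stratified 2:1 allocation, unstructured covariance, s_e 2 and R² 20% gave:

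| Fixed effects | Mean reported SE | Actual spread | Type I error |
|---|---|---|---|
| As in the SAP | 0.0794 | 0.0739 | 4.1% |
| Plus strata main effects | 0.0794 | 0.0739 | 4.1% |
| Plus strata-by-time | 0.0714 | 0.0738 | 5.7% |

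A second simulation, also at R² 20%, gave 0.079 reported against 0.0715 actual (type I error 3%). Adding stratum-by-time brought the reported SE to 0.0716 (5%). The closed-form 0.0724 lies between the two spreads, and the Monte Carlo error on the first is about 0.0739/√2000 = 0.0017. Main effects change nothing because they do not enter the treatment-by-time contrast.

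**2. Covariance too simple, no random slopes.** Under compound symmetry the model assumes s_e²/Sxx + s_b²/11 per patient.

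- s_b 0.3, s_e 2.5: true/reported SE = √(0.1417 / 0.0598) = 1.54. A nominal 5% test would reject 2 × (1 − Φ(1.96/1.54)) = 20% of the time under no effect.
- s_b 0.7, s_e 1.5: √(0.5086 / 0.0631) = 2.84, rejecting 49%.

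With slopes scaled to SD 7.5 at week 48, reported/true SE (type I error in brackets) is:

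| Working covariance | s_e 1 | s_e 2 | s_e 3 |
|---|---|---|---|
| Compound symmetry | 0.33 (52%) | 0.40 (43%) | 0.51 (31%) |
| Toeplitz | 0.81 (11%) | 0.88 (9%) | 0.93 (7%) |
| AR(1) | 0.67 (19%) | 0.99 (5%) | 1.18 (2%) |
| Unstructured or random slope | 1.00 | 1.00 | 1.00 |

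**3. Can a fallback arise?** To week 72 there are 14 post-baseline points, so an unstructured matrix has 14 × 15/2 = 105 parameters for a subgroup of about 100 patients. Non-convergence there is a practical possibility.

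**The case against.** The strongest reply is that the only repeated-measures covariance the SAP chooses is unstructured. That contains the random-slope covariance as a special case, so the standard errors are valid without random slopes. Compound symmetry is the last of three fallbacks, and those are written for the primary model. This stands. A reader might infer that leaving out random slopes is itself the defect, or that the slope p-value will be far too small. The documents support neither. What they support is that the structure is unstated for this model.

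A reader might also infer that adjustment buys precision equivalent to a larger trial. It does not: the estimator's spread hardly moves (0.0739 against 0.0738), because stratified allocation has already balanced the arms. What changes is the reported width. The two faults also pull in opposite directions, so they cannot be added up.

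Nor does the SAP name a slope test. It promises slopes and their difference, and the planned output is a descriptive table (14.2.6) not marked for topline. The rejection rates above apply only if a test or interval is reported. The endpoint is outside the testing hierarchy and SAP 5.6 treats it as exploratory.

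Finally, the gain from the strata may be small. Progression is dichotomised within an eligible range of 0.35–1.5 points per month, and of riluzole the protocol says "It is estimated that about 90% of the patients included in this study will concomitantly receive riluzole treatment", leaving that factor little variance to explain. This is why the low end of the range is near 1%.

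None of this supplies the missing specification. The variable list is explicit and shorter than the primary model's, the protocol leaves methods for these endpoints to the SAP, and SAP section 6 does not mention the difference.

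**Conclusion.** The point holds as a minor specification fault. The slope model ignores both randomisation strata, unlike the other adjusted analyses. With an adequate covariance, its reported standard error is therefore too wide by roughly 1–20%, if the strata explain 5–30% of slope variance. The missing covariance statement leaves open a much larger error in the other direction: under compound symmetry without random slopes, the true error would be about 1.5–2.8 times the reported one. That depends on a choice the plan has not made. All magnitudes assume complete data and the variance inputs listed above; dropout was not modelled. The primary analysis and the confirmatory sequence are unaffected.

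**What to change.** Before unblinding, replace the slope sentence in SAP 5.6.2 with a full model statement:

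- time as a continuous variable, so that a slope is defined;
- a random intercept and random slope per patient, or a named unstructured covariance;
- the listed terms (treatment, baseline value, time, treatment-by-time) plus riluzole stratum, progression stratum and progression-by-time, with riluzole-by-time optional;
- a sentence that the primary model's simpler fallback structures are not used here without a random slope.

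The strata-by-time terms do the work on interval width; strata main effects alone would not. No data, visits or patients are added, and no confirmatory analysis changes. The cost is an SAP edit and the matching program.

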### **Time to event - change from baseline or death**

Time to event, being a change from baseline of 3, 6, 9 and 12 points or death in ALSFRS-R score over 48 or 72 weeks, respectively, will be calculated and summarized by median values with 95% confidence intervals. In addition, the Hazard Ratio with 95% CI will be presented. Comparisons between treatment groups will be done using a Logrank test.

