## 2.4 Sample size

The sample size estimation is based on the primary endpoint: the change from baseline in ALSFRS-R score after 48 weeks. A difference of 3.0 points between FAB122 treatment arm and placebo is assumed with a (pooled) standard deviation of 7.5 and an allocation ratio of 2:1 (FAB122:Placebo). With these assumptions, a total sample size of 300 (200 patients on FAB122 and 100 on placebo) is needed to achieve 90% power to detect the difference of 3.0 points between the two treatment groups at a 5% (2-sided) level of significance.

For further details on the background of these assumptions, refer to the protocol.

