### **‘Survival Time’**

‘Survival Time’, i.e. time to death or time to reaching the criteria for respiratory insufficiency is the other key secondary endpoint. The criteria for respiratory insufficiency are defined as tracheostomy or initiation of non-invasive ventilation for more than 20 hours a day for more than 10 consecutive days, over 48 weeks or 72 weeks, respectively. Descriptive statistics (median and Q1/Q3 quartiles with 95% confidence intervals) and Kaplan-Meier curves will be provided. The difference between oral FAB122 and placebo will be assessed using restricted mean survival time (RMST) analysis for the time point week 48 (and another one for week 72 for the subgroup of 100 patients), adjusting for the stratification variables. The RMST analysis provides robust estimates even when the proportional hazard function is violated.

SAS PROC LIFETEST with option RMST will be used for this analysis.

In addition, a Cox regression model and a stratified log-rank test will also be applied as supportive analysis, including factors for treatment and stratification variables. Patients that complete the study and those that discontinue due to reasons other than death or due to reaching the criteria for respiratory insufficiency will be considered censored.

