### **Overall Survival**

Proportion of patients alive (survival rate) after 24, 48 and 72 weeks for full group and subgroup as available will be presented by treatment groups and overall. Kaplan-Meier plots will be presented, and treatment groups will be compared using a log-rank test.

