### **Staging of disease progression**

Data from staging of disease progression (King's scaling system, MiToS) after 12, 24, 60, 72 weeks as compared to baseline will be presented per visit by treatment group and overall, in summary tables using frequency and percentages. Frequency and percentages of patients showing a decline of  $\geq 1$  stage from baseline will be presented as well.

Kaplan-Meier curves will be created to present time to decline of  $\geq 1$  stage from baseline in both staging systems over 48 weeks or 72 weeks, respectively. A log-rank test will be used to determine the difference between study arms. Patients lost to follow-up will be censored. Days of maintaining the baseline stages will be presented per treatment arm and group/subgroup, including differences between treatment groups.

See section 9.1 for relevant derivations for King's scaling system and MiToS.

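### The log-rank tests for time to functional decline and for staging ignore the randomisation strata: valid but conservative, with some power lost if pre-study slope is prognostic

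*SAP*

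**What the plan says.** Protocol section 4 stratifies randomisation by ALSFRS-R slope from first symptoms to screening (below 1.0 versus 1.0 or more) and by riluzole use.

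Four analyses in SAP 5.6.2 name a log-rank test without strata or covariates:

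- Time to a 3-, 6-, 9- or 12-point decline or death: "Comparisons between treatment groups will be done using a Logrank test". A hazard ratio with 95% CI is also promised, with no model named.
- Staging (King's and MiToS): "A log-rank test will be used to determine the difference between study arms".
- Overall survival: "treatment groups will be compared using a log-rank test".
- Progression-free survival: worded the same way as overall survival.

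Elsewhere the SAP does use the strata. The primary MMRM (SAP 5.6.1) includes both factors. For the key secondary endpoint of survival time, RMST adjusted for the strata comes first, and "a Cox regression model and a stratified log-rank test will also be applied as supportive analysis".

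No general rule in SAP 5.1 or 5.6 adds strata to the four analyses. Protocol 11.3.4.3 leaves the method for the other secondary endpoints to the SAP. SAP 5.6 classes every endpoint outside the hierarchy as exploratory.

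**The concern.** The SAP says stratified where it means it, so a programmer following the text would run these four tests unstratified.

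When randomisation balances a prognostic factor and the test ignores it, two things follow. The variance formula overstates the chance variation between arms, so the test rejects too seldom under the null. The unadjusted hazard ratio is also pulled towards 1.

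The issue is sharpest for time to functional decline, because one stratum is the earlier slope of the very scale that defines the event. MiToS is derived from ALSFRS-R items (SAP 9.1), so the same mechanism plausibly applies to staging.

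At stake are some power, and a clearly defined effect estimate, on analyses that support the primary result.

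**Working it through.** **The plan's own figure.** SAP 2.4 states: "A difference of 3.0 points between FAB122 treatment arm and placebo is assumed with a (pooled) standard deviation of 7.5", with 2:1 allocation, "at a 5% (2-sided) level of significance". Placebo n = (1 + 1/2) × (1.960 + 1.282)² × 7.5² / 3.0² = 98.5, so 99, and the total is 3 × 99 = 297 against 300 stated. At 200/100 the standard error is 7.5 × √(1/200 + 1/100) = 0.919. Then 3.0/0.919 − 1.960 = 1.306, which gives 90.4% power. The figure reproduces. It concerns the primary endpoint only; the documents give no power, event count or hazard ratio for the four log-rank analyses.

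**What the documents say about prognostic strength.** Eligible slopes run from 0.35 to 1.5 points per month (protocol 5.2). The stratum midpoints are (0.35 + 1.0)/2 = 0.675 and (1.0 + 1.5)/2 = 1.25, a ratio of 1.25/0.675 = 1.85. This is an indirect guide to a fast-versus-slow hazard ratio near 2, not an estimate of it.

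**Event frequency.** Placebo decline is taken as 1 point per month (protocol 11.2), so about 11 points by week 48. Small declines should be common; a 12-point decline much less so. Deaths are expected below 17% at 52 weeks (SAP 5.2).

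**Simulation.** Inputs from the documents: 300 patients, 2:1, four strata, about 90% on riluzole (protocol 8.3.1), and two-sided 5%, borrowed from the primary endpoint. Assumptions: blocks of 6, exponential times, censoring at 48 weeks, no dropout, riluzole not prognostic, 20% or 35% fast progressors, placebo risk 80% for decline and 17% for death. There were 3,000 trials per scenario. The statistic is U²/V compared with 3.84, with U and V summed within strata for the stratified version. Ranges run over the two fast-progressor shares.

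| Event, treatment HR | Fast vs slow HR | Plain | Stratified |
|---|---|---|---|
| Decline, 0.67 | 1 | 80–82% | 80–82% |
| | 1.5 | 79–81% | 79–82% |
| | 2 | 77–78% | 79–81% |
| | 3 | 70–73% | 80% |
| Decline, 0.75 | 2 | 49–51% | 55% |
| | 3 | 43% | 51–54% |
| Death, 0.67 | 3 | 25% | 26% |
| Death, 0.50 | 3 | 52–55% | 54–56% |

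The gains for decline are 2.2 to 5.6 points at a fast-versus-slow HR of 2 and 7.0 to 11.0 points at 3. For death no scenario gains more than 1.5 points.

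**Type I error** (4,000 trials, 30% fast). With common events and a fast-versus-slow HR of 1, 2 and 3, the plain test rejects 5.4%, 4.0% and 3.5%; the stratified test 5.4%, 5.1% and 5.0%. With 17% risk the plain test rejects 4.8–4.9% and the stratified test 4.9–5.5%.

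**Rarer events and the 72-week subgroup** (treatment HR 0.7, 25% fast).

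- 300 patients, 50% placebo risk: 50.1 to 50.3% at a fast-versus-slow HR of 1.5, 48.9 to 50.4% at 2, and 45.0 to 50.2% at 3.
- 100 patients, 85% placebo risk: 34.7 to 33.6% at 1, 31.2 to 31.6% at 1.5, and 30.3 to 32.2% at 2.

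Staging was not simulated.

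**The case against.** The strongest reply is that nothing confirmatory turns on this. The hierarchy holds ALSFRS-R at week 48, CAFS and survival time (SAP 4.1). None of the four tests is in it, no power is claimed for them, and the plain test does not inflate type I error. The main functional analysis already adjusts for both strata. All of that stands, and it sets the severity.

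A reader might infer that all four tests lose power. The documents do not support that for overall or progression-free survival: at the expected death rate the difference is at most about 1.5 points. The progression-free composite (death, tracheostomy or prolonged non-invasive ventilation) is also the same as survival time, which already has a stratified log-rank test. What remains there is an inconsistency: one composite, tested with strata in one place and without in another.

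A reader might also take the 7 to 11 points as the expected loss. That needs a fast-versus-slow hazard ratio of about 3, which the documents do not give; the eligible slope range points nearer 2.

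Finally, stratifying is not quite a one-word change. With about 90% on riluzole, roughly 0.10 × 300 = 30 patients fall in the no-riluzole strata, and 0.10 × 100 = 10 in the 72-week subgroup. At an assumed 25% fast progressors, the smallest subgroup cell holds 2 or 3 patients. In that subgroup, stratifying gains little and costs about a point if the strata are not prognostic. This objection stands and shapes the fix.

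**Conclusion.** The omission is real in all four analyses. It has a power consequence for time to functional decline and plausibly for staging. For common decline events the unstratified test loses roughly 2 to 6 points at a fast-versus-slow hazard ratio of about 2 and 7 to 11 at about 3. The loss is under 1 point at 1.5 and nil at 1. It shrinks for rarer thresholds such as 12 points and in the 72-week subgroup. These sizes rest on assumed prognostic strength, stratum shares, event rates and treatment effects, so the exact loss cannot be derived from the documents.

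For overall and progression-free survival the reason to change is consistency. It would be wrong to read the point as an invalid test, an inflated error rate or a threat to the trial's main conclusion: the plain test errs on the conservative side, and the primary analysis, sample size and hierarchy are untouched. Severity is minor.

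**What to change.** In SAP 5.6.2:

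1. Specify the log-rank tests for time to ALSFRS-R decline, staging, overall survival and progression-free survival as stratified by slope group and riluzole use.
2. State that the hazard ratio for time to ALSFRS-R decline comes from a Cox model stratified the same way.
3. Fix a sparse-stratum rule before unblinding, for example stratifying by slope alone if the no-riluzole cells are too small. State how it applies in the 72-week subgroup.

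The cost is a few lines of SAP text and small programming changes. No new data, visits or patients are needed. If slope proves not to be prognostic, power in the full group is essentially unchanged.
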